7.1. Univariate and Bivariate Distributions

In general, the number of observations, mean, median, standard deviation, minimum, and maximum will be calculated for continuous variables. The number of decimal places will be up to plus two decimal places. Frequencies and percentages will be calculated for categorical data. Distribution of continuous variables and proportions of categorical variables will be tabulated by treatment group, and t-test and chi-square tests will be performed to evaluate if these variables are balanced across the 2 intervention groups.

Baseline is defined as the randomization visit.

7.2. Description of Baseline Data

Demographic details (e.g., age, sex, race, ethnicity, marital status, military service), medical history (e.g., co-morbidities), information on index attempt, psychometric measures, and baseline labs will be evaluated overall, by intervention group, by diagnosis of Bipolar Disorder or Major Depressive Disorder, and by enrollment site.

7.3. Description of Follow-up Assessment Data

Details on titration process, concomitant medications, pattern of service use, clinical events such as hospital re-admissions, emergency department admissions, suicide reattempts, psychometric measures, will be evaluated overall and by intervention group.

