The incidence and severity of adverse reactions from lithium are related to its serum concentrations and to individual patient sensitivity, generally occurring more frequently and with greater severity at higher lithium concentrations. According to the American Hospital Formulary Service (AHFS) Drug Information Service (2012), about 75% of people experience some side effects when they begin lithium. The most frequent side effects include nausea, loose stools, thirst, increase in urination, shakiness of the hand, headaches, sweating, fatigue, decreased concentration, rash, and dry skin. For most people, these are mild and limited to beginning of lithium treatment. The prevalence of some side effects is described below:

Nervous system: Lithium can cause a hand tremor in almost 50% of people who start taking the medicine, but it persists for one year in less than 10%. Feelings of weakness or a loss of strength can occur in about 30% of people who start lithium, but it persists in about 1%.

Gastrointestinal effects: Symptoms like nausea or vomiting, decreased appetite, loose stools or diarrhea and abdominal discomfort occur in 10-30% of people who start lithium; they persist for up to 1-2 years in 1-10%.

Kidney effects: Increased urination with increased thirst and fluid intake occurs in 30-50% of people who start lithium. By 1-2 years, these symptoms decrease to between 10-30%.

Metabolic effects: Lithium can lead to increases in Thyroid Stimulating Hormone in about 30% of people, clinically significant decreases in thyroid function in 1-4% and goiter in about 5%.

Heart effects: Lithium can cause changes in the electrocardiogram in about 20-30%, but these are usually of no clinical significance. Rarely, lithium can cause arrhythmias or changes in cardiac conduction, usually in people with preexisting cardiac disease.

Skin effects: Dry skin is the most common skin-related side effect of lithium. Rashes occur in about 1%.

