A recent meta-analysis of adverse effects observed during long term administration of lithium (McKnight et al., 2012) should be noted even though the study drug is intended for only one year. The synthesis found decreases in glomerular filtration rate and in renal concentrating ability, increases in TSH and clinical hypothyroidism, increases in calcium, in PTH, and weight. It found no increased hair loss or skin disease. Contrary to FDA and other warning sources, it found no increase in congenital malformations but the number of cases was too few to be definitive.

Discontinuation and Withdrawal

That lithium might prevent suicide and suicide-related behaviors is suggested by comparisons of patients currently receiving lithium and those who have discontinued lithium (Muller-Oerlinghausen et al., 1992; Nilsson, 1990, 1999; Schou, 1998; Tondo et al., 2000, 2001), comparisons of behaviors before, during and after lithium treatment (Tondo et al., 1997, 1998), and comparisons of patients taking lithium and other medications. Suicide related behaviors may be more frequent during the first year after discontinuation of lithium than afterwards (Tondo et al., 1997, 1998). The available data do not allow a distinction between an unmasking of suicide-related behavior when lithium is discontinued versus a withdrawal phenomenon. However, there have been suggestions that the increase in the onset of mania, depression, and suicide-related behaviors is lower when lithium is discontinued gradually, over a period of two weeks or longer (Baldessarini et al., 1999a; 1999b).

These issues will be addressed by including information about discontinuation in the consent form, gradual tapering of lithium whenever subjects discontinue treatment, and individualized clinical management at the end of the study.

Drug-Drug Interactions

Potential drug-drug interactions are listed on Table 5 ("Lithobid", n.d.). These can result either from effects on the renal excretion of lithium and modifications in lithium levels, or from effects on end-organ sensitivity to other drugs. With most medications with potential drug-drug interactions, a patient may be on a drug with potential interaction with lithium as long as there is close monitoring and regular lithium levels obtained.

Drug-Disease Interactions

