Notification of Local Hospital Leadership	Site Study Staff	HIPAA, VHA Directive 1605.01, VHA Handbook 1200.05, Certificate of Confidentiality	Remind local hospital leadership that release of information regarding study-related matters, including unblinding, with any persons outside the study team is prohibited.
Disclosure of information about mental health care, but not information about research participation , to the family	Mental Health Provider (Note: this activity occurs outside of the study protocol, but is provided as a recommendation).	HIPAA, VHA Directive 1605.01, Certificate of Confidentiality	Local policies and procedures will vary. Consult Privacy Officer and other hospital leadership. Provide forms and assist family in completing the forms to facilitate their information seeking. Do not provide any information regarding study-related matters, including unblinding, with any persons outside the study team.

PROCEDURES

Activity	Responsible Party	Considerations/ Requirements	Recommendation
Completion of SAE forms	CSPCRPCC Study Staff	Protocol	Any other outstanding SAE forms should be closed out with the resolved option.
Completion of study forms	Site Study Staff	Protocol	Complete end of study form
Study visit entry into CPRS	Site Study Staff	Protocol, VHA Handbook 1200.05, Certificate of Confidentiality	-Include clinically relevant information (e.g., "participant expired") -Do not to include information about the study (e.g., "participant completed suicide") -Cause of death should be ascertained by medical records and/or death certificate (should not entered into CPRS, should be entered into DataLabs)

Determination of lithium levels: Close surveillance is essential to patient safety. This includes determination of lithium levels, renal function, thyroid function, hematological measures, electrolytes, and electrocardiograms (EKGs) and meticulous attention to concomitant drugs which might increase toxicity. Our protocol meets or exceeds published guidelines for monitoring patients on lithium.

QT Corrected (QTc) Interval: Due to potential lengthening of the QTc, all randomized participants will receive an electrocardiogram (EKG) on a minimum of four study time points:

1. at screening,
2. once during the titration phase,
3. once during steady state, and
4. at the end of study or early termination.

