7. Managing or reporting of adverse events or serious adverse event, and when questions arise, in consultation with the Site Physician, Clinical Research Pharmacist, Study Chair, or Study Director.

Definitions

For CSP#590, AE and SAEs will be collected using the International Conference on Harmonisation (ICH) Clinical Safety Data Management (ICH-E2A) and CSP Global Standard Operating Procedure (SOP) 3.6.2 definitions as follows:

Adverse Events: An AE is any untoward physical or psychological occurrence in a human subject participating in research. An AE can be any unfavorable and unintended event, including an abnormal laboratory finding, symptom, or disease associated with the research or the use of a medical investigational test article. An AE does not necessarily have to have a causal relationship with the research.

Serious Adverse Events: An SAE is an adverse event that results in:

- Death
- A life-threatening experience,
- Inpatient hospitalization
- Prolongation of hospitalization,
- Persistent or significant disability/incapacity,
- Congenital anomaly/birth defect, or
- Requires medical, surgical, behavioral, social, or other intervention to prevent such an outcome.

Relatedness: Relatedness involves an assessment of the degree of causality between (or attributed to) the *study intervention* and the event. Site investigators are charged with making an assessment of relatedness based on their clinical judgment and experience. The assessment of relatedness provided by the site investigator is used by the sponsor (CSP) to determine if an AE/SAE represents an alteration or change in the safety profile of the study intervention. All AE/SAEs with a reasonable causal relationship to the investigative treatment may be considered “related”. A definitive relationship does not need to be established.

Adverse Events and Serious Adverse Events Reporting Requirements

Adverse Events: Only adverse events possibly or definitely related to the study intervention will be reported. Documentation of this assessment may be recorded on a worksheet or source document. The lithium carbonate formulation used in CSP #590 is a commercially available product prescribed for bipolar disorder. Lithium has a well characterized adverse effect profile and there is no evidence suggesting this agent will demonstrate a different adverse event profile in CSP#590 from the one already known.

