				T 1	T 2-3	T 4	T 5-6	M 2-5	M 6	M 7-8	M 9	M10,11	Early D/C			
Estimated time per visit	2 hrs	2 hrs	1.25hrs	1hr	45min	1.25hr	45min	1hr	1.25hr	1hr	1hr	1hr	1hr	1.75hr	1.75hr	30min
Phone contact allowed ⁺								Yes		Yes		Yes				Yes
Eligibility Screening																
Informed Consent ⁺⁺	X	X														
Review Incl/Excl. Criteria (S12)	X	X														
Demog. and military history (B02, B03)		X														
Medical history reviewed (B04)			X													
Psychiatric history reviewed (S01)	X		X													
Medications and treatments reviewed (S03)	X	X	X	X	X	X	X	X	X	X	X	X	X	X	X	X
MH Provider concurrence documentation obtained	X	(X)														
Primary Care Provider awareness documentation obtained ⁺⁺⁺	X	(X)														
Medical Assessments																
Physical Exam (B01)		X												X	X	
Vital Signs (B01, T04)		X	X	X	X	X	X	X	X	X	X	X	X	X	X	
EKG ⁺⁺⁺⁺ (S09)		X		X (once during titration)				X (once during steady state)						X	X	
Creatinine (S10, T02)		X		X	X	X	X	X	X		X			X	X	
CBC, electrolytes, calcium (S10, T01)		X				X			X					X	X	
TSH, T4 (S10, T02)		X				X			X					X	X	
Pregnancy test as appropriate (S10, T01)		X	X	X	X	X	X	X	X	X	X	X	X	X	X	
Interim history (B05)			X	X	X	X	X	X	X	X	X	X	X	X	X	X
Enrollment																

Randomization (S12)			X												
---------------------	--	--	---	--	--	--	--	--	--	--	--	--	--	--	--

Study Medication	Eligibility Evaluation	Eligibility Confirmation	BL	T 1	T 2-3	T 4	T 5-6	M 2-5*	M 6	M 7-8	M 9	M 10-11	Early D/C	End of Study	F/U (30 days)
Lithium level (T02)				X	X	X	X	X	X		X				
Adherence (T03, T05)				X	X	X	X	X	X	X	X	X	X	X	
Adverse events, (SAEs and AEs) (using lithium side effects checklist) (B13, T02)			X	X	X	X	X	X	X	X	X	X	X	X	X
Planned dose adjustment				X	X	X	X								
Dispense study medication++++			X	X	X	X	X	X	X	X	X	X	(X)	(X)	
Current Treatment Info.															
Medications (S03)	X		X	X	X	X	X	X	X	X	X	X	X	X	
VA record review	X		X	X	X	X	X	X	X	X	X	X	X	X	X
Service use based on the Cornell Service Index (B05)			X	X	X	X	X	X	X	X	X	X	X	X	X
Psychiatric Measures															
MINI (S11)	X														
PCL (B12)		X													
SCID SUD (S05)	X														
OMC (S06)	X														
UBACC (S04)	X														
CSSRS-lifetime version suppl with SIS for index attempt (S07, S08)	X														
CSSRS-last visit version supple with SIS f/u for attempts (B06, S08)		X	X	X	X	X	X	X	X	X	X	X	X	X	X
PHQ-9 (B07)			X	X		X		X	X	X	X	X	X	X	X
ISS (B08)			X	X		X		X	X	X	X	X	X	X	X
Audit C (B09)			X	X				Month 3	X		X		X	X	

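### The SAP specifies no by-arm analysis of follow-up creatinine/eGFR, TSH/T4, calcium or QTc, so these known lithium effects are compared between arms only through reported adverse events

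*SAP*

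**What the plan says.** The protocol expects lithium to act on these measures. Section XII (Side Effects and Adverse Reactions) states: "Lithium can lead to increases in Thyroid Stimulating Hormone in about 30% of people". It adds clinically significant falls in thyroid function in 1-4%, and EKG changes in about 20-30%, usually without clinical significance. It also cites a meta-analysis of long-term use that found "decreases in glomerular filtration rate and in renal concentrating ability, increases in TSH and clinical hypothyroidism, increases in calcium". Section XIV gives the reason for the EKG schedule: "Due to potential lengthening of the QTc, all randomized participants will receive an electrocardiogram (EKG) on a minimum of four study time points".

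The SAP's treatment of the resulting data is as follows.

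- **SAP 7.2:** "psychometric measures, and baseline labs will be evaluated overall, by intervention group". This is the only place where laboratory values are named for analysis by arm.
- **SAP 7.3:** the follow-up list opens with "Details on titration process, concomitant medications, pattern of service use, clinical events such as hospital re-admissions" and continues to emergency admissions, reattempts and psychometric measures. It has no laboratory or EKG item.
- **SAP 7.4:** summaries of adverse events, plus hospitalization, reattempt and mortality rates.
- **SAP 8.3.5:** closed-session tables D1 to D7 hold event rates, event counts and deaths.
- **SAP 9:** tables X4 and X5 are baseline only.
- **SAP 11:** the minimum content of the final report names no follow-up laboratory or EKG value.

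For events, Protocol XV says of non-serious AEs: "Only adverse events possibly or definitely related to the study intervention will be reported". SAEs are collected whatever their relatedness.

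**The concern.** When a trial measures organ function on a schedule in both arms because the drug is known to change it, the natural harm analysis compares those measurements between arms. Under this plan a change in eGFR, TSH or calcium enters the results only if a site turns it into an adverse event. If it is non-serious, the site must also judge it at least possibly related. A moderate shift across the whole lithium arm could pass without generating events. Attribution by blinded staff also adds noise: Protocol VIII.F tells sites that, when in doubt, they should assume the participant is on lithium, which plausibly adds related events on placebo and blurs the contrast.

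At stake is the harm side of the benefit-risk judgement for an adjunctive drug. If these analyses are not pre-specified, the choice of test, visit and cut-off will be made after unblinding.

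**Working it through.** No figure in the plan is in dispute, so there is none to reproduce. The check sets the schedule against the analyses, then illustrates what the data could show.

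**Step 1. Collected against analysed** (Protocol Table 6 and XIV; SAP 7 to 9 and 11)

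| Measure | Scheduled after randomisation | By-arm follow-up analysis in SAP | Stated AE threshold |
|---|---|---|---|
| Creatinine/eGFR | Titration visits, months 2-5, 6 and 9, exit | None | None |
| TSH/T4 | Fourth titration visit, month 6, exit | None | None |
| Calcium | Fourth titration visit, month 6, exit | None | None |
| QTc | Once in titration, once at steady state, exit | None | Above 450 ms (men) or 460 ms (women) |

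Exit means end of study or early termination. For a completer with six titration visits (assumed), creatinine is scheduled up to 6 + 4 + 1 + 1 + 1 = 13 times after randomisation, or 14 with the pre-treatment value. TSH/T4 and calcium are each scheduled 3 times and EKG at least 3 times. The number of post-baseline by-arm analyses of these values named in the SAP is 0.

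**Step 2. Numbers available.** There are 931 per arm (Protocol VII), with 40% dropout spread uniformly over the year.

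- Month 6: 931 × 0.80 = 744.8, about 745 per arm.
- Month 12: 931 × 0.60 = 558.6, about 559 per arm.

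These are upper bounds, because they ignore participants who stop study drug but stay in follow-up. Protocol VIII.C allows for up to 20% stopping drug. If that is in addition to dropout (an assumption), month 12 has 559 × 0.80 = about 447.

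**Step 3. Mean eGFR change.** The 95% half-width is 1.96 × SD × √(2/n). The SD of 10 to 15 is assumed; the documents give none.

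- n = 745: 1.02 to 1.52 mL/min/1.73m2.
- n = 559: 1.17 to 1.76.
- n = 447: 1.31 to 1.97.

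**Step 4. Raised TSH.** The lithium rate of 30% is from Protocol XII, or 0.30 × 744.8 = about 223 participants at month 6. The placebo rate is assumed. At 5% on placebo and n = 745, the half-width is 1.96 × √[(0.30×0.70 + 0.05×0.95)/745] = 3.6 percentage points. Across assumed placebo rates of 5-20%, power at two-sided 5% is at least 99% with 745 per arm and at least 97% with 559.

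**Step 5. Decreased thyroid function.** The lithium rate of 1-4% is from Protocol XII; the placebo rate of 0.5-1% is assumed. With p̄ the mean of the two rates, power = Φ{[Δ − 1.96√(2p̄(1−p̄)/n)] / √[(p₁(1−p₁)+p₂(1−p₂))/n]}.

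| Lithium v placebo | n = 745 | n = 559 |
|---|---|---|
| 4% v 1% | 96.1% | 89.6% |
| 2% v 1% | 35.5% | 27.9% |
| 1% v 0.5% | 20.0% | 16.1% |

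Mean shifts and common abnormalities are therefore well estimated. Whether the rarer clinical event can be resolved depends on where in 1-4% the true rate lies.

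**The case against.** The plan does provide for some comparison of these harms, and four stronger readings that a reader might infer are not supported.

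- **That renal, thyroid, calcium and QTc harm is not compared between arms at all.** SAP 7.4 tabulates event type and MedDRA class by arm, and closed-session tables D5 and D6 show related non-serious AEs and SAEs by organ class and treatment. Protocol XV counts an abnormal laboratory finding as a possible AE, and Protocol XIV makes QTc above the threshold one.
- **That only events judged related reach the results.** This filter applies to non-serious AEs, and possible relatedness is enough. All SAEs are collected. Protocol XIV does not say whether the QTc reporting rule overrides the filter.
- **That the DMC cannot see these values.** It may request formats (Protocol XV), and its tables are revised at its request (SAP 8.2). Protocol XIX also has it review participants with lithium levels of 1.3 or above, including the role of eGFR, although SAP 8.3 lists no table for this. The values are not planned for routine display, but they are available.
- **That the scheduled data would answer the question cleanly.** Measurement depends largely on staying on drug. Persistent QTc prolongation leads to withdrawal under Protocol XIV, so later EKGs are missing selectively.

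It can also be said that SAP 7.1 already tabulates continuous and categorical variables by treatment group. That sentence names no variable or visit and is framed as a balance check; where the SAP means laboratory values, it says baseline. The protocol does present the monitoring as individual patient safety and calls lithium's adverse-effect profile well characterised, and no study objective concerns these laboratory values. Those points explain the gap but do not fill it. Event counts do not show graded change.

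**Conclusion.** The gap is real and should be closed before unblinding. The SAP names no by-arm analysis of post-baseline creatinine/eGFR, TSH/T4, calcium or QTc, although all are measured repeatedly because lithium is known to affect them. The between-arm comparison of these harms rests on reported events alone, with the relatedness filter on the non-serious ones.

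This conclusion follows from the text and depends on no assumed figure. The precision and power figures are illustrations: the eGFR SD and all placebo rates are assumptions, and 745 and 559 per arm are upper bounds. The primary efficacy analysis is unaffected.

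**What to change.** Add to SAP 7.4, by arm:

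1. **Change from the last pre-treatment value**, as a between-arm difference with 95% CI, adjusted for that value, for creatinine/eGFR, TSH, T4, calcium and QTc. Use the scheduled laboratory visits; for QTc, use the titration, steady-state and end-of-study/early-termination EKGs. Define the pre-treatment value explicitly: SAP 7.1 calls the randomization visit baseline, but Table 6 places these tests at the ICF 2 visit.
2. **Numbers and percentages with any on-treatment value beyond a limit.** Use limits already in the documents (eGFR below 60; QTc at or above 450/460 ms and at or above 500 ms) for counting only. For TSH and calcium use the laboratory range, where reference ranges are captured. Show these counts in the DMC closed session as well.
3. **Measurement and missingness.** State that values are mostly on-treatment and report the number measured per arm and visit.

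The protocol passages on testing after study drug stops must also be reconciled. Section XIV says EKGs and blood draws are not required except at the 30-day visit, while Table 7 shows them only at the early-discontinuation visit.

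The cost is mainly SAP text and programming, since Table 6 already assigns these measures to forms S09, S10, T01 and T02. One item needs checking. Protocol XIII lists creatinine, TSH and T4 for the central laboratory but does not mention calcium, and no passage says that site reference ranges are recorded.

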7.4. Safety Data

Safety information to be collected for this study include description of the event, distinction between serious and non-serious adverse event, severity and expectedness of the event, relatedness to the study intervention, and outcome of the event. In addition, data on all events will be classified using the Medical Dictionary for Regulatory Activities (MedDRA) (Version 9.0) coding dictionary.

Safety data will be collected for all consented subjects from the date the first consent was signed up to 13 months post randomization for related non-serious adverse events, and all serious adverse events. If the subject terminates from the study prior to 13 months post randomization date, collection of safety data will cease on termination date.

For reporting to the DMC and inclusion in the final report safety data will be aggregated for the ITT analytic sample only as described in **3.3**. Data will be summarized as follows.

- Frequency and percentages of related non-serious and all serious adverse events overall and by intervention group
- Frequency and percentages of all unique subjects with non-serious and serious adverse events overall and by intervention group
- Rates of non-serious and serious adverse events overall, by intervention group, and by center, calculated as # events/ person-time in years
- Tabulation of event type, MEDRA classification, severity, expectedness, relatedness and outcome of all events overall and by intervention group
- Overall hospitalization, suicide reattempt, and mortality rates at 1 year overall and by intervention group

8. Data Monitoring Committee Reports

Data and study progress will be monitored by the study executive committee and by the Data Monitoring Committee (DMC). The DMC will review the study progress and safety semi-annually with additional meetings and communications as needed. All reports will be generated using SQL and SAS.

